7.5.2 Physical Examination (Maternal Subject)

A full physical examination of the maternal subject will be performed at randomization and at Day 15/End-of-Treatment visit. The physical examination of the maternal subject comprises examination of general appearance, central and peripheral nervous system, head and neck (including ears, eyes, nose, mouth, and throat), cardiovascular system, respiratory system, gastrointestinal system, lymphatic system, urinary system, breasts, skin, and musculoskeletal system.

7.6 Handling of Biological Samples

A detailed description of all sample collections and shipment procedures will be included in a separate laboratory manual.

All biological samples will be analyzed at central laboratories and will be maintained in storage after the end of the trial. Destruction will take place within 2 years after reporting of the trial. For all biological samples collected in the trial, it applies that analyses beyond those described in the protocol can only be performed after obtaining the required approvals. The processes related to handling of biological samples will be described in the informed consent forms (ICFs), and biobank/data protection legislation including local legislation will be adhered to.

8 ADVERSE EVENTS

8.1 Adverse Event Definition

An AE is any untoward medical occurrence in a subject participating in a clinical trial. It includes:

- Any unfavorable and unintended sign, symptom or disease temporally associated with the use of the IMP, whether or not considered to be caused by the IMP
- AEs commonly observed and AEs anticipated based on the pharmacological effect of the IMP
- Any laboratory abnormality, vital sign or finding from physical examination assessed as clinically significant by the investigator [note: findings from assessments and examinations done during screening are not AEs but are recorded as medical history]
- Accidental injuries, reasons for any change in medication (drug and/or dose), reasons for any medical, nursing or pharmacy consultation or reasons for admission to hospital or surgical procedures

Overdoses, medication errors and technical malfunctions of IMP will be captured by the e-CRF and will be reviewed by Ferring Pharmacovigilance on an ongoing basis.

Pre-treatment Adverse Event for Maternal Subjects

A pre-treatment AE for a maternal subject is any untoward medical occurrence arising or observed between informed consent and administration of the IMP.

Treatment-emergent Adverse Event for Maternal Subjects

A TEAE for a maternal subject is any AE occurring after start of the IMP and before the Day 15/End-of-Treatment visit. A pre-treatment AE or pre-existing medical condition that worsens in intensity after start of IMP and before the Day 15/End-of-Treatment visit is also considered treatment emergent.

Pre-treatment Adverse Event for Infants

A pre-treatment AE for an infant is any untoward medical occurrence arising or observed between the signing of the parental informed consent and the infant's first exposure to MoM expressed during maternal subject's treatment period.

Treatment-emergent Adverse Event for Infants

A TEAE for an infant is any AE occurring from the infant's first exposure to MoM expressed during maternal subject's treatment period until the infant's last exposure to MoM expressed during maternal subject's treatment period (i.e., the last milk sample expressed during maternal subject's treatment with IMP is either consumed by the infant or discarded). A pre-treatment AE or pre-existing medical condition that worsens in intensity during the interval stated above is also considered treatment emergent.

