6.4.4 Day 15/End-of-Treatment Visit

End-of-Treatment assessments are performed on Day 15 or the day after the maternal subject's last dose of IMP in case of premature discontinuation. Day 15/End-of-Treatment visit can be postponed a maximum of 2 days.

Maternal subject-related activities:

- Weigh the milk collected since the Day 10 visit (if applicable) and record corresponding weights for each milk expression session (this can also be performed any day when the maternal subject brings collected milk to the trial center)
- Review dosing and milk expression documentation for completeness and compliance
- Perform physical examination
- Measure vital signs (sitting blood pressure and heart rate)
- Collect blood sample for safety laboratory parameters ([Table 6](#)) analysis
- Record concomitant medications
- Collect and record AEs
- Perform drug accountability, including weighing used IMP and collection of all used and unused IMP
- Instruct maternal subject that milk expression information should continue to be collected through the end of Day 17

Infant-related activities:

Collect the following data from hospital records for all treatment days as available since last visit:

- Record body weight
- Record infant enteral feeds (volume of MoM and formula/donor milk fed to the infant)
- Record concomitant medications
- Collect and record AEs including information on morbidity events of special interest (Section 8.4)

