7.2.9 Safety Laboratory Parameters (Maternal Subjects)

Blood samples for safety laboratory evaluations of clinical chemistry and hematology will be collected at screening and at Day 15/End-of-Treatment visit. The clinical chemistry and hematology analyses will be performed by a central laboratory. Safety laboratory parameters are listed in [Table 6](#).

Table 6 Safety Laboratory Parameters

Clinical Chemistry	Hematology
Alanine aminotransferase	Hematocrit
Albumin	Hemoglobin
Alkaline phosphatase	Mean cellular volume
Aspartate aminotransferase	Mean corpuscular hemoglobin content
Glucose	Mean corpuscular hemoglobin concentration
Calcium	Platelet count
Chloride	Red blood cell count
Cholesterol	White blood cell count with differential count
C-reactive protein	White blood cell morphology
Creatinine	
Gamma-glutamyltransferase	
Phosphate	
Potassium	
Sodium	
Total bilirubin	
Urea (blood urea nitrogen)	

The investigator will review the laboratory results and evaluate and document whether the results are clinically significant or non-significant.

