7.5 Other Assessments

7.5.1 Vital Signs (Maternal Subject)

Vital signs include blood pressure and heart rate. Systolic and diastolic blood pressure and heart rate will be measured for maternal subjects at randomization, Day 3, Day 10 and Day 15/

End-of-Treatment visits. Vital signs will be measured while maternal subject is in sitting position after resting for at least 3 minutes. Vital signs should always be measured before blood sampling.

All recordings will be performed using validated standard equipment. Vital sign assessments may be repeated for quality reasons and the repeat will be used for analysis.

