8.2.2 Recording of Adverse Events

The investigator must record all AEs in the Adverse Event Log provided in each subject's e-CRF with information about:

- Adverse event
- Date and time of onset (time can be omitted, if applicable)
- Intensity
- Causal relationship to IMP
- Action taken to IMP
- Other action taken
- Date and time of outcome (time can be omitted, if applicable)
- Outcome
- Seriousness

Each of the items in the Adverse Event Log is described in detail in the following sections.

Adverse Events

AEs should be recorded as diagnoses, if available. If not, separate signs and symptoms should be recorded. One diagnosis/symptom should be entered per record.

If a subject suffers from the same AE more than once and the subject recovers in between the events, the AEs should be recorded separately. If an AE changes in intensity, a worst-case approach should be used when recording the event, i.e., the highest intensity and the longest duration of the event.

However, if an AE with onset before the first IMP administration (i.e., a pre-treatment AE) changes in intensity, this must be recorded as 2 separate events. The initial AE should be recorded with outcome ‘not recovered’ and the date and time of outcome is when the intensity changed. The second AE should be recorded with date and time of onset when the intensity changed.

Note the following: A procedure is not an AE; the reason for conducting the procedure is. Hospitalization is not an AE; the reason for hospitalization is. Death is not an AE, but the cause of death is (an exception is sudden death of unknown cause, which is an AE).

Date and Time of Onset

The date of onset is the date when the first sign(s) or symptom(s) was first noted. If the AE is an abnormal clinically significant laboratory test or outcome of an examination, the onset date is the date the sample was taken or the examination was performed.

Intensity

The intensity of an AE must be classified using the following 3-point scale:

Mild: Awareness of signs or symptoms, but no disruption of usual activity

Moderate: Event sufficient to affect usual activity (disturbing)

Severe: Inability to work or perform usual activities (unacceptable)

Causal Relationship to IMP

The possibility of whether the IMP caused the AE must be classified as one of the following:

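### The maternal TEAE window closes before the Day 15/End-of-Treatment visit, so adverse events first found by that visit's bloods, examination or vital signs cannot enter the TEAE tables

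*Combined protocol and SAP*

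**What the plan says.** Section 8.1 defines the maternal treatment-emergent window: "A TEAE for a maternal subject is any AE occurring after start of the IMP and before the Day 15/End-of-Treatment visit". An earlier event or condition that "worsens in intensity after start of IMP and before the Day 15/End-of-Treatment visit is also considered treatment emergent", so onset and worsening share one closing point. The same section makes a laboratory, vital-sign or examination finding an AE once the investigator judges it clinically significant.

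Section 8.2.2 sets the onset for an AE that is itself an abnormal test or examination result: "the onset date is the date the sample was taken or the examination was performed". It also allows the onset time to be left out.

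On the schedule:

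- Section 7.2.9: "Blood samples for safety laboratory evaluations of clinical chemistry and hematology will be collected at screening and at Day 15/End-of-Treatment visit".
- Section 7.5.2: "A full physical examination of the maternal subject will be performed at randomization and at Day 15/End-of-Treatment visit". Table 3 (footnote c) places the first of these before randomization.
- Section 7.5.1: "Systolic and diastolic blood pressure and heart rate will be measured for maternal subjects at randomization, Day 3, Day 10", and again at the Day 15/End-of-Treatment visit.
- Section 6.4.4: "End-of-Treatment assessments are performed on Day 15 or the day after the maternal subject's last dose of IMP in case of premature discontinuation". The visit may be postponed by up to 2 days.

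On reporting, sections 9.6.3 and 9.8.2 summarize maternal AEs as TEAEs only. The search for nasal tolerability events in section 7.2.8 is also run on TEAEs. Section 8.2.3 collects maternal AEs through the Day 18/Follow-up visit, so collection runs past the TEAE window.

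**The concern.** The frequency and intensity of maternal AEs is a secondary endpoint (section 2.2). Section 1.3 describes this as the first trial with merotocin exposure beyond 45 hours. The End-of-Treatment visit holds the one scheduled laboratory and full-examination check after dosing, and section 2.2 names markedly abnormal laboratory changes at that visit as a secondary endpoint. The protocol therefore uses that visit's bloods to judge the safety of treatment, while its TEAE definition keeps AEs arising from those bloods out of the AE tables.

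At stake is the by-arm comparison of maternal AEs. An event found at this check would be missing from the tables by system organ class and preferred term, causality, intensity and seriousness. A nasal finding first seen at the examination, which covers the nose, would also fall outside the nasal tolerability search.

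**Working it through.** The plan gives no figure to reproduce. The check applies the section 8.1 window and the section 8.2.2 onset rule to each scheduled post-dose maternal safety assessment.

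**Step 1: classify a finding first made at the visit.** A clinically significant finding is an AE (8.1). Its onset is the date of the sample or examination (8.2.2), which is the visit itself. The visit is not before the visit, so the event is not a TEAE. It arose after the first dose, so it is not a pre-treatment AE either. It belongs to neither category.

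**Step 2: count scheduled post-dose assessments inside the window.**

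| Assessment | Scheduled after first dose | Before the End-of-Treatment visit | Inside / scheduled |
|---|---|---|---|
| Safety laboratory (7.2.9; Table 6: 16 chemistry + 9 hematology = 25 parameters) | End-of-Treatment | none | 0 / 1 |
| Full physical examination (7.5.2; 11 areas) | End-of-Treatment | none | 0 / 1 |
| Vital signs (7.5.1) | Day 3, Day 10, End-of-Treatment | Day 3, Day 10 | 2 / 3 |

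**Step 3: check early discontinuation.** The End-of-Treatment visit then falls on the day after the last dose, subject to the 2-day allowance, and the bloods and examination are again at the visit. The counts in step 2 do not change.

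**Step 4: check the tables.** Section 9.8.2 lists seven summaries: all TEAEs, by causality, leading to death, by intensity, adverse drug reactions by intensity, serious events, and leading to withdrawal. All 7 of 7 are limited to treatment-emergent events.

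**Step 5: events dated on the visit day without a time.** Because the time may be omitted, an AE carrying only the visit date cannot be placed before or after the visit. No rule in the documents assigns it.

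**Step 6: size.** The documents give no rate of AEs first detected by these assessments. Assume 1% to 5% of 100 randomized subjects, both arms together:

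- 100 × 0.01 = 1 event
- 100 × 0.05 = 5 events

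**Not affected.** Day 3 and Day 10 vital signs, unscheduled tests before the visit, and any event whose first sign or symptom was noted earlier all stay inside the window, even if first reported at the visit.

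**The case against.** The strongest reply is that little information is lost. Laboratory values are summarized by time point and arm, with change from baseline and a markedly-abnormal table (9.6.3). Examination, blood pressure and heart rate have shift tables by arm (9.8.3), and all AEs are listed (9.8.2). Subject protection does not depend on TEAE status: the Safety Committee reviews AEs and laboratory data at least every third month (3.5), and SAEs are reported within 24 hours (8.5.2). All of this stands. It limits the harm to tabulation, but none of those by-arm tables carries the investigator's AE, causality, intensity and seriousness assessments.

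The affected set is also narrow. Only findings with no earlier sign or symptom take the visit date, so most nasal complaints would keep an earlier onset. A finding at a completer's Day 15 visit can hardly have led to withdrawal, and the death table is very unlikely to change. The parameter and area counts describe what is examined, not events lost. These points are fair and keep the size small.

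A pharmacological defence is that the half-life is 0.56 hours (1.3), so Day 15 is off drug. The cut-off does not follow that logic. Dosing stops at the end of Day 14 even if the visit is postponed, so a symptom on Day 16 before a postponed visit is a TEAE, while a blood result from an on-time Day 15 visit is not.

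Finally, section 9 refers further methods to a separate SAP, which is not among the documents and might contain a rule. Handling of missing onset times could reasonably be left to it. The boundary itself is protocol text, and a SAP that included the visit would contradict section 8.1.

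**Conclusion.** The concern holds. Under sections 8.1 and 8.2.2 as written, AEs first detected by the End-of-Treatment bloods, examination or vital signs are excluded from every maternal TEAE summary, and nothing in the documents repairs this. A named secondary safety endpoint is under-counted by construction: 0 of 1 post-dose laboratory checks, 0 of 1 post-dose examinations and 2 of 3 post-dose vital-sign checks can contribute a newly detected TEAE.

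The number of events is probably small: 1 to 5 across both arms, on the assumed rate of 1% to 5%. The primary efficacy analysis, AE collection and ongoing safety oversight are unaffected. It should be fixed, because the definition works against the purpose of the visit and the correction is cheap. The missing rule for untimed events would, taken alone, be only a gap in detail.

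**What to change.** In section 8.1, define the maternal TEAE window, for both onset and worsening, as running from first IMP administration through and including the Day 15/End-of-Treatment visit. State that findings from that visit's blood samples, physical examination and vital signs are included. Add a derivation rule to the SAP that an AE dated on the visit day without an onset time counts as treatment-emergent. Optionally, summarize AEs with onset after that visit and through Day 18 separately as post-treatment events.

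The cost is two sentences in section 8.1 and one SAP rule, made before unblinding. No new data are needed, since maternal AEs are already collected through Day 18. The one consequence is that maternal TEAE counts may rise slightly.

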8.2 Collection and Recording of Adverse Events

8.2.1 Collection of Adverse Events

The sources of AEs cover:

- The subject's response to questions about her health (a standard non-leading question such as 'How have you been feeling since your last visit?' is asked at each visit). (This is only applicable to maternal subjects)
- Symptoms spontaneously reported by the subject. (This is only applicable to maternal subjects)
- Investigations and examinations where the findings are assessed by the investigator to be clinically significant changes or abnormalities
- Other information relating to the subject's health becoming known to the investigator (e.g., hospitalization)

8.2.2 Recording of Adverse Events

The investigator must record all AEs in the Adverse Event Log provided in each subject's e-CRF with information about:

- Adverse event
- Date and time of onset (time can be omitted, if applicable)
- Intensity
- Causal relationship to IMP
- Action taken to IMP
- Other action taken
- Date and time of outcome (time can be omitted, if applicable)
- Outcome
- Seriousness

Each of the items in the Adverse Event Log is described in detail in the following sections.

Adverse Events

AEs should be recorded as diagnoses, if available. If not, separate signs and symptoms should be recorded. One diagnosis/symptom should be entered per record.

If a subject suffers from the same AE more than once and the subject recovers in between the events, the AEs should be recorded separately. If an AE changes in intensity, a worst-case approach should be used when recording the event, i.e., the highest intensity and the longest duration of the event.

However, if an AE with onset before the first IMP administration (i.e., a pre-treatment AE) changes in intensity, this must be recorded as 2 separate events. The initial AE should be recorded with outcome ‘not recovered’ and the date and time of outcome is when the intensity changed. The second AE should be recorded with date and time of onset when the intensity changed.

Note the following: A procedure is not an AE; the reason for conducting the procedure is. Hospitalization is not an AE; the reason for hospitalization is. Death is not an AE, but the cause of death is (an exception is sudden death of unknown cause, which is an AE).

Date and Time of Onset

The date of onset is the date when the first sign(s) or symptom(s) was first noted. If the AE is an abnormal clinically significant laboratory test or outcome of an examination, the onset date is the date the sample was taken or the examination was performed.

Intensity

The intensity of an AE must be classified using the following 3-point scale:

Mild: Awareness of signs or symptoms, but no disruption of usual activity

Moderate: Event sufficient to affect usual activity (disturbing)

Severe: Inability to work or perform usual activities (unacceptable)

Causal Relationship to IMP

The possibility of whether the IMP caused the AE must be classified as one of the following:

Reasonable possibility: There is evidence or argument to suggest a causal relationship between the IMP and the AE. The AE may occur as part of the pharmacological action of the IMP or may be unpredictable in its occurrence

Examples:

- AEs that are uncommon but are known to be strongly associated with IMP exposure
- AEs that are not commonly associated with IMP exposure, but the event occurs in association with other factors strongly suggesting causation, such as a strong temporal association with the IMP or the event recurs on rechallenge with the IMP

No reasonable possibility: There is no reasonable evidence or argument to suggest a causal relationship between the IMP and the AE

Examples:

- Known consequences of the underlying disease or condition under investigation
- AEs common in the trial population, which are also anticipated to occur with some frequency during the course of the trial, regardless of IMP exposure

Action Taken to IMP

The action taken to the IMP in response to an AE must be classified as one of the following:

- No change (medication schedule maintained or no action taken)
- Discontinued
- Interrupted
- Dose reduced

Other Action Taken

AEs requiring therapy must be treated with recognized standards of medical care to protect the health and well-being of the maternal subject.

If medication is administered to treat the AE, this medication should be entered in the Concomitant Medication Log. Infant concomitant medication needs to be reported in the electronic system only once (dose and frequency may be omitted), as a complete list of medications (including dose and frequency, as applicable) may be printed from the hospital records (de-identified) and sent to the sponsor following discharge of the infant from the NICU if more information is later needed.

Date and Time of Outcome

The date and time the subject recovered or died.

Outcome

The outcome of an AE must be classified as one of the following:

- Recovered (fully recovered or the condition has returned to the level observed at initiation of trial treatment)
- Recovered with sequelae (resulted in persistent or significant disability/incapacity)
- Recovering
- Not yet recovered
- Fatal

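### Section 8.2.2 opens a second record when a pre-treatment AE improves, so an AE that drops a grade but persists on treatment can be counted as treatment-emergent

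*Combined protocol and SAP*

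**What the plan says.** Section 8.2.2 has two recording rules. The general one keeps a single record: "If an AE changes in intensity, a worst-case approach should be used when recording the event". The exception is for events that began before dosing: if "an AE with onset before the first IMP administration (i.e., a pre-treatment AE) changes in intensity, this must be recorded as 2 separate events". On such a split, the first record is closed as not recovered at the time of the change, and "The second AE should be recorded with date and time of onset when the intensity changed". Neither sentence of the exception gives a direction of change.

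Section 8.1 defines treatment emergence in two steps. The first is by timing: "A TEAE for a maternal subject is any AE occurring after start of the IMP and before the Day 15/End-of-Treatment visit". The second deals with what was already there, whether an AE from before treatment or a "pre-existing medical condition that worsens in intensity after start of IMP and before the Day 15/End-of-Treatment visit is also considered treatment emergent". The infant definition has the same structure. It opens "A TEAE for an infant is any AE occurring from" the infant's first exposure to milk expressed during the mother's treatment, and then adds the same worsening sentence for that interval.

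Section 9.8.2 tabulates TEAEs for mothers and infants and flags pre-treatment AEs in the listings. Section 9.6.3 separately summarizes all infant AEs by treatment group and by intensity.

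**The concern.** The recording rule is wider than the definition it feeds: 8.2.2 acts on any *change*, 8.1 on *worsening*. Suppose a moderate event that began after consent becomes mild after the first dose. The log then holds a mild event with an on-treatment onset, and partial recovery looks like a new event.

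The worsening sentence in 8.1 does not clearly prevent this. It says such events are *also* treatment emergent, which adds to the timing sentence and does not restrict it. The items that 8.2.2 requires in the Adverse Event Log include neither a link between the two records nor the intensity at first dose, so the log as described gives no sure way to tell a step down from a step up. Section 9.8.2 has no rule for a second record of lower grade.

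At stake are the TEAE tables and the secondary endpoints on frequency and intensity of AEs, in the first trial with merotocin exposure beyond 45 hours (section 1.3).

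**Working it through.** The plan states no figure on this point, so the check is textual. The inputs are the split rule and its onset date (8.2.2), the two-step TEAE definitions (8.1), the medical-history rules (8.1, and Table 4 note c in 6.1), the outcome categories (8.2.2) and the planned summaries (9.6.3, 9.8.2).

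**Mothers, case by case**

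| Course of the condition | Records | TEAE by onset date | TEAE by worsening sentence |
|---|---|---|---|
| (a) Starts after consent, worsens after first dose | Two, second on treatment | Yes | Yes |
| (b) Starts after consent, drops a grade after first dose, persists | Two, second on treatment | Yes | No |
| (c) Changes grade between consent and first dose only | Two, both pre-treatment | No | No |
| (d) Resolves fully | One, outcome recovered (the 3-point scale has no resolved grade) | No | No |
| (e) Present before consent, or found at screening | Medical history, no AE split | No | Only if it worsens |

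Only case (b) gives conflicting answers. The outcome list in 8.2.2 suggests that it was not intended: recovery there includes return to the level at the start of trial treatment, so a record opened because intensity fell below that level would already meet the recovery criterion at its own onset.

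**Infants**

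The same cases apply, with two additions.

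1. The summary of all infant AEs in 9.6.3 is not restricted to TEAEs. Both halves of a split AE enter it whichever TEAE rule is used. The number of infants with an AE does not change, because the first half already counts; the number of events rises by one, at the lower grade.
2. The anchors differ. Section 8.2.2 ties the split to the first IMP administration; section 8.1 ends the infant's pre-treatment period at first exposure to treatment-period milk. An infant AE that starts between the two is pre-treatment under 8.1, yet on the literal wording of 8.2.2 it stays on one worst-case record. A later worsening would then carry a pre-exposure onset and could be missed.

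**Illustration of size (all inputs are assumptions)**

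Let p be the true risk of at least one TEAE, and s the proportion of subjects with at least one case (b) record, equal in both arms and independent of p. Then reported risk = 1 − (1 − p)(1 − s). Take p = 20% and 30%, a risk ratio of 1.5 and a difference of 10 points.

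- s = 10%: 1 − 0.80 × 0.90 = 28%; 1 − 0.70 × 0.90 = 37%; ratio 1.32, difference 9 points.
- s = 25%: 1 − 0.80 × 0.75 = 40%; 1 − 0.70 × 0.75 = 47.5%; ratio 1.19, difference 7.5 points.
- s = 40%: 1 − 0.80 × 0.60 = 52%; 1 − 0.70 × 0.60 = 58%; ratio 1.12, difference 6 points.

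Since only case (b) contributes, the low end is the more plausible, but nothing in the documents confirms a value.

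**The case against.** The best defence is that 8.1 speaks specifically about pre-treatment AEs and names worsening. A programmer who follows that sentence would not flag an improved record, and an AE is by definition an untoward occurrence, which a step down is not. Section 9 leaves further methodology to a SAP that is to be ready before unblinding; no separate SAP text was supplied, so a suitable flag rule there cannot be excluded. This stands to the extent that miscounting follows from deriving the flag by onset date and is not a result the protocol states. It does not remove the conflict between the two sections, or the extra infant event in the 9.6.3 summary.

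A reader might infer that resolving postpartum and neonatal conditions in general will fill the TEAE tables. The documents do not support that. Infant conditions from birth to consent are medical history, as are screening findings; full recovery stays on its own record; and a change before first dose gives a second onset that is also pre-treatment.

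A reader might also infer that a true safety signal would be hidden. That goes too far. The illustration concerns the risk of any TEAE. In a table by preferred term, dilution arises only where the same term also has improving pre-treatment records. The planned safety output is descriptive, and an investigator could judge an improving pre-dose event unrelated.

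Finally, splitting at every change of grade has a merit: it preserves the intensity at dosing. Any narrowing of the rule has to keep that information.

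**Conclusion.** The mismatch is real and worth correcting, within narrow limits. It concerns AEs that begin between consent and first dose (infant: first exposure to treatment-period milk), then fall in grade but continue on treatment. For these, 8.2.2 creates a record that meets the timing sentence of the TEAE definition although the event improved; for infants the record also enters the summary of all infant AEs.

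The size cannot be determined from the documents. The rule is the same in both arms, so the expected effect is similar extra background counts in each and a modest dilution of contrasts. That rests on the affected proportion being small and balanced. The conclusion on TEAE counts also rests on the flag being derived from logged onset, which the protocol neither prescribes nor rules out.

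**What to change.** 1. In 8.2.2, limit the second record to worsening after the first IMP administration; for infants, to worsening after first exposure to treatment-period milk. The infant wording also reconciles the two anchors. Improvements stay on the existing record under the worst-case rule.
2. Record the intensity at first exposure for every AE ongoing at that time.
3. In 8.1 and 9.8.2, state that a continuation record is a TEAE only if its intensity exceeds the intensity at first exposure. The comparison must not be with the worst pre-treatment intensity: an event that was severe after consent, mild at first dose and moderate on treatment did worsen after the start of IMP, but would be missed against a record held at severe.
4. For data already entered, do not count records opened only for improvement as separate AEs or as TEAEs.

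The cost is a few sentences in the protocol or SAP, a small change to the e-CRF guideline to capture the intensity at first exposure, and one pass to re-flag existing second records. Assessments and visits do not change.
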